3.4.3. Exploratory endpoints

- Per-patient medical conditions, information, and demographics as described in the procedure sections
- *Phase 1 only*– Engineering/optimization images and associated image data from clinically indicated MRI follow-up for unexpected findings

4. DESIGN OF RESEARCH STUDY

4.1. Type of Research Study

4.1.1. Study Type

This is a two-phase, single-site, open-label, prospective research study involving human neonate and infant subjects. This study is designed as a two-phase clinical trial with a feasibility and optimization phase (Phase 1) and controlled image collection study (Phase 2).

Phase 1 is being conducted to optimize and calibrate the device for subsequent data collection in Phase 2 of this study. Both parts may be used for regulatory submission purposes, including CE mark and submissions to other global regulatory authorities in other countries.

- | | | |
|-------------------------|-------------------------------------|---|
| Open-Label |  | All MR scanner configurations are known to researchers and subjects |
| Blinded |  | |
| Double-Blinded |  | |
| Single site |  | There is one investigational site |
| Multi-site |  | |
| Randomization Procedure |  | |
| Not randomized |  | Randomization is not required, as there is no comparative hypothesis testing |
| Single arm |  | There are no comparison or control groups |
| Comparator |  | |
| Parallel |  | |
| Crossover |  | |
| Prospective |  | Subjects are enrolled and then undergo study procedures |

4.1.2. Rationale for Two-Phase Study Design

This study is being conducted in two phases, as follows:

Phase 1: The first phase (Phase 1) is a feasibility and optimization assessment that cannot be conducted in any other population and is designed to allow collection of clinical image and associated data as well as to assess image quality, workflow, and usability in human subjects. The results from Phase 1 will be considered in deciding whether to continue to Phase 2 and, if Phase 2 is conducted, the most appropriate device configuration. Phase 1 data is not primarily intended for regulatory submission but may, if determined necessary by the Sponsor, be disclosed to regulatory authorities in support of regulatory submission.

Phase 2: Phase 1 will be followed by a sequential second phase (Phase 2) to collect human images and data intended to assess sample images and associated per-subject data for use in regulatory submissions.

Images and data from both Phase 1 and Phase 2 may be used to support future engineering activities.

4.2. Controls and Minimization of Bias

The following bias control methods are being employed in this study:

- a. Selection bias will be limited by consecutively enrolling subjects meeting the inclusion/exclusion criteria

- b. Spectrum bias will be limited by using a population expected to be representative of the general population at the investigational site, without regard for gender, race, or ethnicity.
- c. Reader bias will be limited by ensuring that evaluators and readers making performance assessments are separate radiologists (not the PI or neonatologist).

5. STUDY SUBJECTS

5.1. Number of Subjects

Subjects will be enrolled in two phases, to achieve thirty (30) datasets in Phase 1 (Feasibility and Optimization) and up to five (5) datasets in Phase 2 (Data Collection) for a total of thirty-five (35) total evaluable datasets in both phases.

To achieve the target of 35 datasets, a total maximum of 60 subjects may be enrolled per the sample size calculation shown in Section 8.1.1 – Sample Size Determination. The minimum number of patients possible will be used to achieve the target number of evaluable datasets.

5.1.1. Quotas by Anatomic Region

The expected 35 evaluable datasets required for this study are set forth in the quota detailed in Table 2 by anatomical region. There is only one anatomical region for this study.

Table 2- Number of evaluable image datasets

Anatomic Region	Approximate number of evaluable datasets required (n)	
	Phase 1 (Feasibility and Optimization)	Phase 2 (Data Collection)
Neurological(Head/Neck/Spine)	30	5

**n* = approximate total number of evaluable datasets

The Sponsor may choose to end either Phase of the Study when adequate datasets are achieved, based on determination made by the Sponsor. Any such determination that would limit enrolment within a phase and/or individual quota group will be communicated in writing to the investigational site. Any such limitations that apply only within a single quota group do not constitute termination of the study.

5.1.2. Special Considerations for Enrolment

The following special considerations apply to subject enrolment in both Phase 1 and Phase 2.

1. **Incomplete Datasets:** Datasets may be incomplete due to factors such as noise, sequence failure, or patient movement. Datasets determined to be incomplete or non-evaluable by the investigator will not be counted towards the total required datasets for the purposes of determining quota fulfilment (per protocol population) but these will be reported in the total patient enrolment in the study final report.

(intent-to-treat population). Both complete and incomplete images and data will be stored and provided to the Sponsor for engineering purposes.

2. **Changes to Quota Requirements during the Study:** The Sponsor reserves the right to change quota or Phase dataset number requirements at its discretion and for any reason within the set patient enrolment maximum. The Sponsor will notify the investigational site in writing of any changes in enrolment quotas.

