6.3.4. Evaluations

Performance Evaluation

Image sets will be labelled according to subject identification number. Images will be evaluated as evaluable (diagnostic) or non-evaluable (non-diagnostic) by two evaluators, and then evaluable images will be read for image quality by a separate reader, as shown in [Figure 2](#).

[figure not shown]

Figure 2– Flowchart of performance evaluation. Determination of evaluable/non-evaluable for diagnostic purposes will be used as the primary performance measure. All secondary Image Quality Assessments will be descriptively summarized.

MR image datasets for each subject will be evaluated twice by two delegated radiologists serving as image evaluators (Evaluator 1 and Evaluator 2) as:

- Evaluable (Diagnostic Quality)⁶, or
- Non-evaluable (Non-Diagnostic quality)

The evaluations and printed name and signature of the image evaluator(s) will be recorded to an Evaluator CRF. In the event that the two evaluators (Evaluator 1 and Evaluator 2) disagree on whether an image is evaluable or non-evaluable, a third medically qualified reader (Reader 1) will arbitrate to provide an evaluable/non-evaluable decision, which will be recorded to the Reader CRF and treated as the final decision for the image set.

Image Quality Assessments

All evaluable images will be further examined by a single reader (Reader 1) that may be the PI or a qualified delegated radiologist for image quality on a 1-5 Likert Scale,⁷ as follows:

- Overall image quality

⁶ An image set may be considered of diagnostic quality if it contains images suitable for diagnosis (not all images views are typically required to be diagnostic based on specific scanning circumstances, so long as applicable views necessary for diagnosis are present)

⁷ Likert Scale of 1-5, where:

- 1 = Very Poor
- 2 = Poor
- 3 = Neutral
- 4 = Good
- 5 = Excellent

Note For image quality assessment, scores of 3, 4, or 5 will be considered diagnostic quality, and scores of 1 and 2 will be considered nondiagnostic quality.

- Image contrast
- Presence of artefacts
- Signal to noise ratio (SNR)
- Tissue contrast
- Fat/water homogeneity
- Additional Sponsor-Requested Assessments
 - CRF fields (10 blank “Assessment Title” lines with associated 1-5 Likert scales) will be provided on the CRF to accommodate Sponsor-requested elements that may be specified for each *MR Procedure Document*

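### Sections 4.2(c) and 5.1.2 do not fit Section 6.3.4 on who decides that a dataset is evaluable: the PI may arbitrate the primary measure, and the investigator's call can keep a finally evaluable dataset out of the quota

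*Combined protocol and SAP*

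**What the plan says.** **Target and endpoints.** Section 5.1 and Table 2 aim at about 35 evaluable datasets: 30 in Phase 1 and up to 5 in Phase 2. Section 3.4.1 lists collection to quota as a primary endpoint item. It lists the proportions evaluable and non-evaluable as the performance item.

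**How evaluability is decided.** Under Section 6.3.4 each subject's dataset "will be evaluated twice by two delegated radiologists serving as image evaluators". If the two disagree, "a third medically qualified reader (Reader 1) will arbitrate to provide an evaluable/non-evaluable decision". The section then fixes the standing of that ruling, "which will be recorded to the Reader CRF and treated as the final decision for the image set". The Figure 2 caption makes this determination the primary performance measure, and Table 3 assigns it to both the reader and the evaluators. Under Image Quality Assessments, the same section describes the person who scores the images as "a single reader (Reader 1) that may be the PI or a qualified delegated radiologist". A footnote lets a set pass as diagnostic although "not all images views are typically required to be diagnostic based on specific scanning circumstances".

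**Bias control.** Section 4.2(c) undertakes that "evaluators and readers making performance assessments are separate radiologists (not the PI or neonatologist").

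**Quota rule.** Section 5.1.2 item 1 says "Datasets determined to be incomplete or non-evaluable by the investigator will not be counted towards the total required datasets". The purpose it gives also names the analysis set concerned: "for the purposes of determining quota fulfilment (per protocol population"). Datasets left out in this way are still reported in total enrolment, which the plan labels intent-to-treat.

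**The concern.** A dataset's evaluability should have one decider and one meaning, and here two statements disagree with Section 6.3.4.

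The first concerns independence. The safeguard in 4.2(c) keeps the PI out of performance assessment. Appendix M, read only for its rationale, explains that the PI and neonatologist may take part in acquiring the scans. If the PI can be Reader 1, the PI can cast the deciding vote on exactly those datasets where two independent radiologists could not agree. The primary measure is then not protected in the way the plan says it is.

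The second concerns counting. The quota is a number of evaluable datasets, but 5.1.2 removes datasets on a determination by the investigator and does not refer to 6.3.4. The final report could then carry a quota count and a per protocol set that disagree with the number of datasets finally ruled evaluable, with no rule for which governs. Extra infants could also be scanned to replace datasets that were in fact evaluable. That would sit badly with the undertaking in Section 5.1 to use as few patients as possible.

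**Working it through.** **Part 1: who may arbitrate**

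1. Section 6.3.4, Performance Evaluation: Reader 1 gives the final decision when the evaluators disagree.
2. Section 6.3.4, Image Quality Assessments: Reader 1 may be the PI.
3. From 1 and 2, the PI may give the final evaluable/non-evaluable decision.
4. Figure 2 caption: that decision is the primary performance measure, so making it is a performance assessment.
5. Section 4.2(c): readers making performance assessments are not the PI.

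Steps 3 and 5 cannot both hold. Only datasets on which the two evaluators disagree are affected. The documents do not say how many to expect.

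**Part 2: which datasets count**

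| Investigator's call (5.1.2) | Final decision (6.3.4) | Counted towards the quota? |
|---|---|---|
| Accepted | Evaluable | Yes |
| Accepted | Non-evaluable | 5.1.2 is silent; it is not an evaluable dataset, so nothing makes it count |
| Incomplete or non-evaluable | Evaluable | No under 5.1.2, although finally evaluable |
| Incomplete or non-evaluable | Non-evaluable | No |

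Only the third row is a conflict that follows from the text.

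**Part 3: size of the third row**

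Inputs: 35 datasets, 82% evaluable and 20% dropout (Section 8.1.1); a cap of 60 (Section 5.1). One dataset per subject is taken as the usual case, as 8.1.1 does.

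The plan's own figure: 0.82N − (0.82N)(0.2) = 0.656N = 35, so N = 35/0.656 = 53.35. The plan states 53, so its figure is reproduced.

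Let *s* be the share of finally evaluable datasets that go uncounted. The expected enrolment needed for 35 counted datasets is N = 35 / (0.656 × (1 − *s*)). The documents give no value for *s*, so a range is assumed.

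| *s* (assumed) | 0.656 × (1 − *s*) | N | Extra over 53.35 |
|---|---|---|---|
| 0 | 0.6560 | 53.35 | 0 |
| 2% | 0.6429 | 54.44 | 1.09 |
| 5% | 0.6232 | 56.16 | 2.81 |
| 10% | 0.5904 | 59.28 | 5.93 |

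In expectation the cap of 60 is reached at *s* = 1 − 35/(0.656 × 60) = 1 − 35/39.36 = 11.1%.

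**The case against.** **Little hangs on the count.** Table 2 calls its numbers approximate, and Phase 2 is a ceiling of five. The sponsor decides when a phase ends and may change the quotas. There is no hypothesis test, and success in Section 8.4 is not tied to the quota. The per protocol label has no analysis attached to it. All of this stands, and it limits the size of the point. It does not remove the inconsistency: in a descriptive study the counts are the result, and Section 3.4.1 makes collection to quota a primary item.

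**The term investigator may be loose.** Table 3 refers to the investigator's experience for an item that only the reader completes, so 5.1.2 might mean the image readers. That is possible, but nothing says so. If it means the PI acting as Reader 1, it runs into 4.2(c).

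**Completeness may be a separate requirement.** Section 5.1.2 describes incompleteness by cause (noise, sequence failure, movement) and does not require every view, so the footnote in 6.3.4 does not contradict it. The sponsor may also want complete sets for engineering use. This stands, so the remedy should not quietly abolish a completeness criterion.

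**The PI option sits under the secondary reads.** It appears under Image Quality Assessments and could have been meant for those alone. But the same label, Reader 1, is used for the arbitrator, and no text separates the two roles.

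**Conclusion.** Wrong as written on both counts, with minor to moderate effect.

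The arbitration conflict is the more important, because it touches the primary performance measure directly: the bias control promised in 4.2(c) is not secured by 6.3.4. The documents do not show that the PI will arbitrate, only that the PI may.

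The counting conflict is real in one direction: a dataset can be left out under 5.1.2 and still be finally evaluable. Under assumed rates of 2% to 10% this costs about 1 to 6 additional infants, within the cap. Those figures rest on the plan's 82% and 20%, on one dataset per subject, and on disagreement rates that the documents do not supply.

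Three stronger readings are tempting and are not supported:

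- A reader might infer that accrual could stop with fewer than 35 finally evaluable datasets because a lenient investigator filled the quota. Section 5.1.2 only excludes. It does not say that a dataset the investigator accepts counts whatever 6.3.4 decides, so no shortfall should be claimed.
- A reader might infer that the count rests on the PI and neonatologist, whom version 7.0 took out of the evaluator role. Section 5.1.2 does not tie the investigator to either of them.
- A reader might infer that the quota count distorts the primary proportion. The evaluability decisions behind that proportion come from 6.3.4, and the quota count does not drive it.

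**What to change.** **Section 6.3.4 and 4.2(c).** State that disagreements on evaluability are settled by a delegated radiologist who is neither the PI nor Evaluator 1 or 2. If the PI option is kept, limit it to the secondary image quality reads and word 4.2(c) to match. The plan already allows Reader 1 to be a qualified delegated radiologist, so no new role is needed. The cost is that such a radiologist must be available for the discordant datasets.

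**Section 5.1.2 item 1.** State that non-evaluable means the final decision under 6.3.4, and that quota and per protocol status follow that decision. If the sponsor wants completeness as a further requirement, define it, record it separately, and report how many finally evaluable datasets were excluded for incompleteness. No extra reads are needed, because 6.3.4 already has both radiologists evaluate each subject's dataset. The cost is that the count waits for the reads and any arbitration. Section 6.3.4 sets no timeline for these, so a few more infants could be enrolled if reads lag. Prompt reading near the target would limit this.

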5.2. Subject Population

Viable neonate and/or infant subjects that meet the inclusion and do not meet the exclusion criteria will be enrolled.

5.3. Protection of Vulnerable Subjects

5.3.1. Vulnerable Subjects

This study involves a vulnerable population (viable neonates and infants), per ISO 14155:2011 that defines a vulnerable subject as any individual whose willingness to volunteer in a clinical investigation could be unduly influenced by the expectation, whether justified or not, of benefits associated with participation or of retaliatory response from senior members of a hierarchy in case of refusal to participate. This definition includes children, such as the neonates and infants included in this study, which would otherwise require consent from a legally authorized representative acting in their best interests.

This study is being conducted to collect images and data on a device intended for use in neonates and infants that could not be otherwise conducted without using this vulnerable population. The Sponsor has conducted previous internal testing using phantoms to evaluate the safety of the device for use on humans.

Protection of these vulnerable subjects is imperative and the following safeguards will be employed:

- a. Only viable, living neonates and infants will be included in this study;
- b. No neonates of uncertain viability or nonviable neonates will be included in this research;
- c. Individuals engaged in the research will have no part in determining the viability of a neonate, and all such determinations will be made according to the standard clinical practice at the investigational site.

5.4. Inclusion Criteria

Subjects will be included that are:

1. Currently admitted for treatment or observation at the investigational site at the time of enrolment;
2. In the weight range less than 5.0 kg (<5.0 kg¹) and more than 0.5 kg (>0.5 kg²);
3. Viable neonates (birth to 1 month of age) or infants (>1 month to two years of age)³;
4. Able to safely undergo an MRI scan, as determined by medically qualified personnel;

¹ <5.0 kg is considered equivalent to <5000.00 g

² >0.5 kg is considered equivalent to >500.00 g

³ 1 month is considered equivalent to 30 days; 2 year is considered equivalent to 729 days or less

5. Have parent(s), guardian(s), or legally authorized representative(s) willing and able to provide written informed consent for the subject's participation;
6. Are of appropriate size and shape to fit into the bore of the magnet, inclusive of all monitoring equipment, if any, necessary for the subject's routine clinical care based on standard of care measurement methods, in accordance with site policies :
 - a. Maximum width (shoulder-to-shoulder measurement) less than eighteen (18 cm).
 - b. Maximum length (head-to-foot measurement) less than sixty (60) cm.

5.5. Exclusion Criteria

Subjects will be excluded that:

1. Have parent(s), guardian(s), or legally authorized representative(s) that require that they accompany the subject into the MR environment that have contraindications to the MR environment or would otherwise be put at undue risk or discomfort, as determined by medically qualified personnel;⁴
2. Have any ferrous or electrical items or non-removable medical devices that are not compatible with MR scanning (including devices labelled as MR Unsafe, MR conditional for which the scanning conditions are not met, or without MR safety labelling that does not satisfy site MR safety requirements) that may pose hazards in the MR scanning or MR environment, in the opinion of the Principal Investigator or medically qualified personnel in accordance with the site's MR Safety policy;
3. Have any contraindications or could otherwise be expected to experience detrimental effects to safety, well-being, or medical care, as determined by the Principal Investigator or medically qualified personnel in accordance with the site's MR Safety policy;
4. Require any scheduled standard of care procedures that are expected to be adversely impacted by participation in this study, in the opinion of the principal investigator or medically qualified personnel; and
5. Have been previously enrolled AND undergone any study procedures under the current study protocol (i.e. the same subject cannot undergo study procedures, including swaddling and/or MR scanning, more than once).

5.6. Screening Subjects for Enrolment

5.6.1. Subject Recruitment

Subjects that are expected to meet the site's MR Safety Policy criteria and any additional supplemental safety policies criteria recommended by the investigator (as per the exclusion criteria) and are otherwise eligible for inclusion will be recruited through a neonatologist, neonatologist fellow, or study staff authorized through written delegation at each investigational site, in accordance with EC/IRB policy.

⁴ If it is not safe for the parent or guardian that wishes to accompany the subject into the MR environment, the parent or guardian may opt not to accompany the subject. In this case, the subject would not be excluded. Subjects would be excluded if it is determined to be potentially unsafe for a parent or guardian to accompany a subject into the MR scan suite, and the parent or guardian is not willing to allow the subject to be scanned alone while he/she waits in another area of the hospital.

5.6.2. Screening for Enrolment

Potential subjects will be identified by the Principal Investigator or other qualified site staff. Informed consent will be obtained for those subjects who agree to participate in the study. Subjects will then be screened for enrolment to ensure the subject is eligible to participate per the inclusion/exclusion criteria, as per the judgement of medically qualified personnel.

Subjects who do not qualify based on inclusion/exclusion criteria will be considered screen failures.

Once a subject is determined to be eligible per the inclusion/exclusion criteria including providing written informed consent, the subject will be considered enrolled and assigned a subject number.

5.7. Duration of Enrolment

The study plans to enrol patients for approximately 24 months.

6. PROCEDURES FOR RESEARCH STUDY

6.1. General Procedures

6.1.1. Quality Control Scans

The study staff conducting the investigational MR scans (scan operator) will conduct regular Quality Control scans using phantom imaging according to the MR system Operator Manual. The results of Quality Control scans will be stored at a secure location at the investigational site and may be reviewed by the Sponsor.

Phantom Scanning

The investigator and/or Sponsor representatives may execute phantom scans that simulate human scanning for the purposes of training, troubleshooting, or other engineering optimization purposes at any time during the study.

Specific Absorption Rate (SAR) Scans

The device is equipped with a predictive SAR model designed to conservatively limit actual SAR exposure in research subjects. The predictive SAR model used on the system is detailed in the technical documentation for the Neonatal MRI device. Each scan session will include sequences designed to generate a range of actual SAR data, which is stored in system logs and subsequently collected by Sponsor engineering representatives. Throughout the study, system log files containing experimentally generated SAR data will be routinely collected, along with relevant clinical data such as patient weight (*as described in subsequent protocol sections*), necessary for future evaluation of the system's predictive SAR model versus actual clinical data in the infant/neonate population.

MR Scan Session Log

In order to account for all MR scan sessions using the investigational MR system, the scan operator will maintain a daily *MR Scan Session Log*. Because this investigational MR scanner may be used for concurrent research protocols, the *MR Scan Session Log*. Appendix E-

Example of MR Scan Log) may also contain entries from other approved studies. For this study, the log will include:

- a. the GEHC-issued study number,
- b. subject number,
- c. date of imaging
- d. MR Procedure Document version number, in applicable
- e. anatomy imaged
- f. comments, if applicable

The log will continue as long as the investigational MR device is housed at the site, and will only be discontinued when all EC/IRB-approved studies are completed and the investigational MR device(s) is/are removed from the investigational site.

Note: All human scans for this study, scans done for any other active EC/IRB-approved studies using this device, and other nonclinical scans (i.e. phantom scans for research, service/maintenance, or training) will be logged. This is done so that the log is consistent with the internal log inside of the system for engineering purposes. The log may contain other columns required by other concurrent protocols and some fields may be marked as not applicable (N/A) for other concurrent protocols.

